6 STATISTICAL METHODOLOGY

6.1 General Considerations

Continuous data will be summarized descriptively including the number of participants (n), mean, standard deviation (SD), median, minimum and maximum. Categorical data will be summarized by frequencies and percentages. Percentages by categories will be based on the number of participants with no missing data, i.e. the percentages for the non-missing categories will add up to 100%.

There are 2 different groups defined based in the randomization group:

- ASP0367 any dose group: Participants randomly assigned to ASP0367.
- Placebo to ASP0367 group: Participants randomly assigned to placebo and who continue into the OLE and receive ASP0367.

Safety analysis and other summaries based on SAF will be presented by analysis group (ASP0367 any dose group or Placebo to ASP0367 group), unless specifically stated otherwise.

All data summarization and analyses will be performed using SAS® Version 9.4 or higher on Linux. Specifications for table, figures, and data listing formats can be found in the TLF specifications.

For continuous variables that are recorded as "<X", "<=X", ">X", or ">=X", the value of "X" will be used in the calculation of summary statistics if otherwise noted. This approach may result in a summary that reflects the presence of an analyte (such as troponin) when in fact the analyte was not detected but reported as less than the lower limit of detection by the assay.

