6.5.2 Clinical Laboratory Evaluation

Quantitative values including hematology, biochemistry, and urinalysis will be summarized using mean, standard deviation, minimum, maximum and median by analysis group at each analysis visit. Additionally, a within-participant change will be calculated as the post-baseline measurement minus the baseline measurement and summarized in the same way. Each laboratory result will be classified as low (L), normal (N), or high (H) at each visit according to the site supplied reference ranges. For the Placebo and ASP0367 groups, baseline values for CK-MM and CK-MB will be defined as the last non-missing observation prior to the first administration of ASP0367.

Frequency tabulations of qualitative clinical laboratory variables (urinalysis) will be presented for each analysis group at each visit.

Additionally, amylase, lipase and troponin elevations above the ULN and 2xULN will be summarized by analysis group. The denominator for each criterion will be the number of participants who have at least one value after the day of first ASP0367 taken to 28 days after the last dose of ASP0367. The number and percentage of participants meeting the criteria by 28 days after the last dose of ASP0367 will be summarized by analysis group.

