6.5.2.1 Liver Safety Assessment

The liver safety assessments will be summarized by the categories below based on the measurements from ALP, ALT, total bilirubin, AST and their combination. These parameters will be based on measurements from a local laboratory. If the baseline value is above ULN then use the baseline value instead of ULN.

- ALT > ULN, > 2xULN, > 3xULN, > 5xULN, > 10xULN, > 20xULN
- AST > ULN, > 2xULN, > 3xULN, > 5xULN, > 10xULN, > 20xULN
- ALT or AST > ULN, > 2xULN, > 3xULN, > 5xULN, > 10xULN, > 20xULN
- ALP > 1.5xULN, 2xULN, 2.5xULN
- Total Bilirubin > 2xULN
- (ALT or AST > 3xULN) and Total Bilirubin > 2xULN
- (ALT or AST > 3xULN) and ALP < 2xULN and Total Bilirubin > 2xULN

The last 2 criteria where 2 or more parameters are evaluated will be with the measurements on the same day or up to 1 day apart.

The denominator for each criterion will be the number of participants who have at least one value after the day of first ASP0367 taken to 28 days after the last dose of ASP0367. The number and percentage of participants meeting the criteria by 28 days after the last dose of ASP0367 will be summarized by analysis group.

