6.8 Additional Conventions

6.8.1 Analysis Windows

Day 1 and Day -1 are defined as the day of start taking the IP and its prior day, respectively. The following analysis window will be used. The data summary by visits will be done following the analysis windows specified in the table below:

Analysis Visits	Scheduled Day in	Analysis Windows (day)
	Protocol	, , ,
Screening	Day -28	-35 to -14
Week 0	Day -2 to 1	-2 to 1
Week 1	Day 8	5 to 13
Week 2	Day 14	14 to 18
Week 3	Day 22	19 to 25
Week 4	Day 29	26 to 42
Week 8	Day 57	43 to 70
Week 12	Day 85	71 to 98
Week 16	Day 113	99 to 126
Week 20	Day 141	127 to 154
Week 24	Day 169	155 to 182
Week 28	Day 197	183 to 210
Week 32	Day 225	211 to 238
Week 36	Day 253	239 to 266
Week 40	Day 281	267 to 294
Week 44	Day 309	295 to 322
Week 48	Day 337	323 to 350
Week 52	Day 365	351 to 378
Week 56	Day 393	379 to 406
Week 60	Day 421	407 to 434
Week 64	Day 449	435 to 462
Week 68	Day 477	463 to 490
Week 72	Day 505	491 to 518
Week 76	Day 533	519 to 560
End of Treatment	Day 533	2 to 560
Follow-up	The last dose + 28	The last dose + 28 days to the last dose +
_	days	35 days

For all analysis visits excluding follow-up visit, the data "by the last dose + 7 days" will be included.

For participants who received ASP0367 on the double blind part, all analysis visits will be used. For participants received placebo on the double blind part, baseline and analysis visit at and after the first ASP0367 taken will be used.

If more than one observation exists within the analysis window, the observation closest to the scheduled visit day will be selected for that visit. If there are two observations that have the same distance from the scheduled day, the value that is after the scheduled day will be selected in the analysis. If more than one observation is made on the same day, an average value if continuous or the worst value if categorical will be included in the analysis.

For Placebo to ASP0367 group, the measurement at week 52 is used as baseline, and for ASP0367 groups, the measurement at week 0 is used as baseline, unless otherwise specified.

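### In the 76-week SAP, the percentages ever above a laboratory threshold are not comparable between ASP0367 any dose and Placebo to ASP0367: follow-up on drug is up to 76 vs 24 weeks (the main cause), and early visits are denser in the randomised group

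*SAP*

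**What the plan says.** All references are to the 76-week SAP unless stated.

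- Section 6.5.2: "amylase, lipase and troponin elevations above the ULN and 2xULN will be summarized by analysis group". Both numerator and denominator run from the first ASP0367 dose to 28 days after the last. A participant counts once if a criterion is ever met, and nothing adjusts for time on drug or number of tests.
- Section 6.5.2.1: "The liver safety assessments will be summarized by the categories below based on the measurements from ALP, ALT, total bilirubin, AST and their combination". It uses the same period and counting rule, but takes its values from a local laboratory. Section 5.2.6 says that safety laboratory tests are done centrally.
- Section 6.1: "Safety analysis and other summaries based on SAF will be presented by analysis group (ASP0367 any dose group or Placebo to ASP0367 group". There is no placebo column in this SAP.
- Section 6.8.1: after the first double-blind dose, the first-month rows are "Week 1 Day 8 5 to 13", "Week 2 Day 14 14 to 18", "Week 3 Day 22 19 to 25" and "Week 4 Day 29 26 to 42". After week 52 (Day 365) the next row is week 56 (Day 393), then every 4 weeks to week 76 (Day 533).
- Section 6.8.1 also states: "For participants received placebo on the double blind part, baseline and analysis visit at and after the first ASP0367 taken will be used".
- Section 1: until protocol version 7.0 the double-blind period was 52 weeks and the extension 24 weeks. No participant was evaluated under version 8.0 or later.

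**The concern.** A percentage of participants ever above a limit rises with the number of times each participant is tested. The two columns differ in length of follow-up on drug and in frequency of testing early on. They would therefore be expected to show different percentages even if the drug carried the same risk in both.

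With no placebo column in this SAP, these two columns are the ones a reader will set side by side. Protocol 2.3.1.3 names cardiac toxicity as an important potential risk, and troponin elevation is part of an adverse-event-of-special-interest definition. A lower figure among the switchers could be taken as reassurance about starting ASP0367 when it reflects fewer weeks and fewer tests.

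**Working it through.** **Inputs.** Scheduled days come from the window table in 6.8.1. The extension is assumed to start at Day 365. One blood draw per listed visit is assumed. The per-draw chance p of exceeding a limit is not in the documents; 0.5% to 5% is assumed, equal in both columns and independent between draws.

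**Step 1: visit counts.** The SAP states no threshold rate, so the figure to reproduce is the schedule.

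- First 28 days on ASP0367: weeks 1, 2, 3, 4 vs week 56, so 4 vs 1.
- First 24 weeks: weeks 1, 2, 3, 4, 8, 12, 16, 20, 24 vs weeks 56, 60, 64, 68, 72, 76, so 9 vs 6.
- Whole on-drug period: the 9 above plus weeks 28 to 76 every 4 weeks (13 visits) vs 6, so 22 vs 6. The follow-up visit makes it 23 vs 7.

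These are maxima for participants who complete.

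**Step 2: source of the difference.** 22 − 6 = 16 extra visits. Of these, 13 lie after week 24 on drug (longer exposure) and 3 are weeks 1 to 3 (denser early visits).

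**Step 3: expected percentage ever exceeding at equal true risk.** With k draws the share is 1 − (1 − p)^k. For example, 1 − 0.95^22 = 67.6% and 1 − 0.95^6 = 26.5%.

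| Period (draws) | p = 0.5% | p = 1% | p = 2% | p = 5% |
|---|---|---|---|---|
| First 28 days (4 vs 1) | 2.0 vs 0.5 | 3.9 vs 1.0 | 7.8 vs 2.0 | 18.5 vs 5.0 |
| First 24 weeks (9 vs 6) | 4.4 vs 3.0 | 8.6 vs 5.9 | 16.6 vs 11.4 | 37.0 vs 26.5 |
| Whole period, as planned (22 vs 6) | 10.4 vs 3.0 | 19.8 vs 5.9 | 35.9 vs 11.4 | 67.6 vs 26.5 |
| Whole period without weeks 1–3 (19 vs 6) | 9.1 vs 3.0 | 17.4 vs 5.9 | 31.9 vs 11.4 | 62.3 vs 26.5 |
| First 24 weeks, shared visits (6 vs 6) | 3.0 vs 3.0 | 5.9 vs 5.9 | 11.4 vs 11.4 | 26.5 vs 26.5 |

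Entries are percentages, ASP0367 any dose vs Placebo to ASP0367. Dropping weeks 1 to 3 alone barely changes the planned comparison. Cutting to 24 weeks alone leaves 9 vs 6. Both steps are needed for equality.

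**Step 4: dependence on persistence.** If an elevation persists once it occurs, the week 4 draw finds it whether or not weeks 1 to 3 were sampled. The part of the gap due to sampling density then shrinks towards zero.

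**Step 5: size in participants.** Final enrolment is not stated. The interim analysis used the first 33 participants across three arms, so about 33 / 3 = 11 on placebo. Assuming all 11 switch, the 24-week gap at p = 5% is (37.0 − 26.5)% × 11 = 1.2 participants. At p = 0.5% it is (4.4 − 3.0)% × 11 = 0.2. The whole-period gap is (10.4 − 3.0)% × 11 = 0.8 to (67.6 − 26.5)% × 11 = 4.5.

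**The case against.** The strongest objections, and what remains of each:

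- *The window table is not a blood-draw schedule, and the version 7.0 schedule is not supplied.* This stands. A draw in weeks 53 to 55 would fall inside the week 52 window (351 to 378) or the week 56 window (379 to 406), so a missing row does not prove a missing draw. Draws at weeks 1, 2 and 3 are nevertheless a fair inference. The version 9.0 schedule collects abbreviated biochemistry at those visits, and Protocol Appendix 6 lists troponin I and T, amylase, lipase and the liver tests in that panel.
- *The liver table may not follow these visits.* This stands until 5.2.6 (central) and 6.5.2.1 (local) are reconciled. Troponin, amylase and lipase are unaffected.
- *The tables are descriptive, and the randomised comparison with placebo is in the 52-week SAP.* Correct. It limits the harm to misreading, but two columns built on different follow-up still invite it.
- *Section 6.5.2 already summarises values and low/normal/high classes at each visit.* Correct, so week 4 can be read against week 56. That does not repair the cumulative percentages at 2xULN or the liver multiples.

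A reader might infer that early sampling alone drives the difference. It does not: weeks 1 to 3 supply 3 of 16 extra visits. A reader might also infer that a brief early rise will be caught in one group and missed in the other. The documents give no duration for such a rise, and Protocol 2.3.1.2 points both ways. Amylase and lipase rises resolved without treatment, and one troponin I rise was a single episode. Another participant's troponin I was still above the limit at a repeat on day 21.

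**Conclusion.** The concern holds as a limit on comparability. The planned percentages for the two columns would be expected to differ at equal true risk, mainly because on-drug follow-up is up to 76 vs 24 weeks and secondarily because early visits are denser for randomised participants. The visit counts come directly from the window table. The percentages rest on one draw per listed visit, full follow-up, independence, and an exceedance rate that the documents do not give; actual counts may be lower because the study was stopped for futility. It would go too far to say that the switchers' early safety was left unobserved, or that sampling density alone biases the table. This is an improvement to a descriptive safety display in a small group, of low to moderate priority.

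**What to change.** Keep the table planned in 6.5.2 and add one for troponin, amylase and lipase:

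- Limit it to the first 24 weeks after first ASP0367 dose, with visits defined in days from that dose.
- Use only the 4-weekly visits both groups share: weeks 4, 8, 12, 16, 20 and 24 on ASP0367 (weeks 56 to 76 for switchers).
- Give the number of samples and the exposure per participant in each column.
- Show week 1 to 3 and unscheduled values separately.

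Reconcile the laboratory source between 5.2.6 and 6.5.2.1, then apply the same layout to the liver table.

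The cost is one extra table per display from data already collected. The matched table omits the week 1 to 3 values, but these remain in the existing table.

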6.5.2.1 Liver Safety Assessment

The liver safety assessments will be summarized by the categories below based on the measurements from ALP, ALT, total bilirubin, AST and their combination. These parameters will be based on measurements from a local laboratory. If the baseline value is above ULN then use the baseline value instead of ULN.

- ALT > ULN, > 2xULN, > 3xULN, > 5xULN, > 10xULN, > 20xULN
- AST > ULN, > 2xULN, > 3xULN, > 5xULN, > 10xULN, > 20xULN
- ALT or AST > ULN, > 2xULN, > 3xULN, > 5xULN, > 10xULN, > 20xULN
- ALP > 1.5xULN, 2xULN, 2.5xULN
- Total Bilirubin > 2xULN
- (ALT or AST > 3xULN) and Total Bilirubin > 2xULN
- (ALT or AST > 3xULN) and ALP < 2xULN and Total Bilirubin > 2xULN

The last 2 criteria where 2 or more parameters are evaluated will be with the measurements on the same day or up to 1 day apart.

The denominator for each criterion will be the number of participants who have at least one value after the day of first ASP0367 taken to 28 days after the last dose of ASP0367. The number and percentage of participants meeting the criteria by 28 days after the last dose of ASP0367 will be summarized by analysis group.

6.5.3 Vital Signs

Vital signs (systolic blood pressure, diastolic blood pressure, and pulse rate) will be summarized using mean, standard deviation, minimum, maximum and median by analysis group and visit. Additionally, a within-participant change will be calculated per visit as the

post-baseline measurement minus the baseline measurement and summarized by analysis group and visit.

6.5.4 Electrocardiograms

6.5.4.1 Routine 12-lead Electrocardiograms

The number and percent of participants with normal, not clinically significant abnormal, and clinically significant abnormal results as assessed by site principal investigator for the 12 lead ECG will be tabulated by analysis group and time point. Continuous 12-lead Electrocardiogram.

For all analyses, replicates at each visit will be averaged for each continuous ECG parameter.

ECG parameters [Heart Rate (bpm), PR Interval (ms), QRS Interval (ms) and QTcF (ms)] read by the central laboratory will be summarized using mean, standard deviation, minimum, maximum and median for each analysis group at each visit, including changes from baseline.

The QTcF interval will be summarized using frequency tables for each visit for values of clinical importance using the range criteria below.

	QTcF Interval Criteria Value (msec)
Normal	\leq 450
Borderline	> 450
Prolonged	> 480
Clinically significant	> 500

QTcF: QT interval using Fridericia's correction.

The QTcF interval will also be summarized by the frequencies of participants with an increase from baseline of clinical importance using the criteria identified below. These summaries will be provided for each visit.

Variable	Change from Baseline
QTcF Interval (msec)	\leq 30
	> 30
	> 60

QTcF: QT interval using Fridericia's correction.

6.5.5 Other Safety-Related Assessment

6.5.5.1 Body Weight

Body weight will be summarized using mean, standard deviation, minimum, maximum and median by analysis group and visit. Additionally, a within-subject change will be calculated per visit as the post-baseline measurement minus the baseline measurement and summarized by analysis group. For Placebo to ASP0367 group, the measurement at week 52 is used as baseline, and for ASP0367 Any Dose, the measurement at Screening is used as baseline.

6.5.5.2 C-SSRS

The results of five questions regarding suicidal ideation, six questions regarding suicidal behavior, suicidal ideation or behavior and self-injurious behavior without suicidal intent will be summarized using number and percent of participants by analysis group at each visit.

6.6 Other Analyses

No analyses will be conducted.

6.7 Interim Analysis

6.7.1 Interim Analysis of Efficacy

The analysis of futility and of efficacy was performed when the first 33 participants completed the efficacy evaluation at week 24 or discontinued as of date the last participant had the week 24 visit, 20-Nov-2023. The change from baseline in distance walked on the 6MWT at week 24 was analyzed using the same MMRM as with the primary endpoint excluding the site group from the model to decide whether the study will continue.

Analysis of Futility

For the futility stop, the study may be stopped if the conditional probability of achieving the criteria below at the final analysis is less than 10%.

Criteria: Lower limit of the 90% CI for the difference is greater than 0 m AND the point estimate of the difference between the ASP0367 75 mg group and the placebo group is greater than 30 m.

In addition to 6MWT at week 24, outputs for participant disposition, demographics and the secondary endpoints 5XSTS, Neuro-QoL Short Form Fatigue score, Neuro-QoL Short Form Lower Extremity Function (Mobility) score, MFIS, PGIC, and PGIS at week 24 were analyzed at the interim analysis.

Analysis of Efficacy

For the efficacy stop, a two-stage group sequential design with Lan-DeMets alpha-spending function determined by means of the O'Brien-Fleming approach was used to preserve the overall two-sided type I error rate of 0.10 between this single interim analysis and the final analysis. If the p-value of the comparison between ASP0367 75 mg and placebo groups at interim analysis is lower than the boundary determined by O'Brien-Fleming approach, efficacy would be considered to be achieved at week 24.

The interim analysis outputs were prepared by an external statistician and presented to the AIDMC who made recommendations about the ongoing conduct of the study. After the AIDMC reviewed the interim analysis results, the AIDMC recommended the study to be stopped because the results of the interim analysis met the criteria for futility. Details of the analysis were defined in the interim analysis plan.

6.8 Additional Conventions

6.8.1 Analysis Windows

Day 1 and Day -1 are defined as the day of start taking the IP and its prior day, respectively. The following analysis window will be used. The data summary by visits will be done following the analysis windows specified in the table below:

Analysis Visits	Scheduled Day in	Analysis Windows (day)
	Protocol	, , ,
Screening	Day -28	-35 to -14
Week 0	Day -2 to 1	-2 to 1
Week 1	Day 8	5 to 13
Week 2	Day 14	14 to 18
Week 3	Day 22	19 to 25
Week 4	Day 29	26 to 42
Week 8	Day 57	43 to 70
Week 12	Day 85	71 to 98
Week 16	Day 113	99 to 126
Week 20	Day 141	127 to 154
Week 24	Day 169	155 to 182
Week 28	Day 197	183 to 210
Week 32	Day 225	211 to 238
Week 36	Day 253	239 to 266
Week 40	Day 281	267 to 294
Week 44	Day 309	295 to 322
Week 48	Day 337	323 to 350
Week 52	Day 365	351 to 378
Week 56	Day 393	379 to 406
Week 60	Day 421	407 to 434
Week 64	Day 449	435 to 462
Week 68	Day 477	463 to 490
Week 72	Day 505	491 to 518
Week 76	Day 533	519 to 560
End of Treatment	Day 533	2 to 560
Follow-up	The last dose + 28	The last dose + 28 days to the last dose +
_	days	35 days

For all analysis visits excluding follow-up visit, the data "by the last dose + 7 days" will be included.

For participants who received ASP0367 on the double blind part, all analysis visits will be used. For participants received placebo on the double blind part, baseline and analysis visit at and after the first ASP0367 taken will be used.

If more than one observation exists within the analysis window, the observation closest to the scheduled visit day will be selected for that visit. If there are two observations that have the same distance from the scheduled day, the value that is after the scheduled day will be selected in the analysis. If more than one observation is made on the same day, an average value if continuous or the worst value if categorical will be included in the analysis.

For Placebo to ASP0367 group, the measurement at week 52 is used as baseline, and for ASP0367 groups, the measurement at week 0 is used as baseline, unless otherwise specified.

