9.4.1 General Considerations

In general, continuous data will be summarized with descriptive statistics (number of participants, mean, SD, minimum, median and maximum), frequency and percentage for categorical data. Percentage by categories will be based on the number of participants with no missing data (i.e., will add up to 100%).

Baseline will be defined as the last non-missing observation prior to first administration of IP, unless otherwise specified.

Demographics and baseline characteristics (age, sex, race and ethnicity, body weight, height and BMI) and genetic abnormality for PMM will be summarized by treatment group and overall for the Safety Analysis Set (SAF).

The number and percentage of participants who complete and discontinue 24 weeks of treatment and reasons for treatment discontinuation will be presented for all randomized participants by treatment group and overall. All disposition details and dates of first and last evaluations for each participant will be listed.

All previous and concomitant treatment and medical history will be listed. Medical history will be coded using MedDRA and will be summarized by system organ class (SOC) and preferred term (PT) by treatment group and overall for the SAF. All IP exposure data will be listed.

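### The 76-week SAP does not tie the placebo-switchers' week-52 baseline to the first ASP0367 dose, so with certain timings an on-drug value can serve as baseline

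*SAP*

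**What the plan says.** The 76-week SAP is a safety-only plan covering the 52-week double-blind part and the 24-week open-label part of protocol version 7.0. For placebo participants who continue into the open-label part, section 6.8.1 says "For Placebo to ASP0367 group, the measurement at week 52 is used as baseline". Section 6.5.5.1 (body weight) and the Table 1 footnote (walking aid use) apply the same week-52 rule.

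Week 52 is an analysis window of days 351 to 378 around scheduled day 365, counted from the first dose of blinded product. With several values in the window, "the observation closest to the scheduled visit day will be selected for that visit". With two equally distant values, "the value that is after the scheduled day will be selected in the analysis". With several on one day, "an average value if continuous or the worst value if categorical will be included in the analysis". The only data cut in this section is seven days after the last dose, and it does not apply to the follow-up visit.

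Three other places bear on this:

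- The key-terms table of the 76-week SAP describes baseline as assessed before participants receive ASP0367.
- Section 6.5.2 of the 76-week SAP gives an explicit pre-drug rule for two analytes only: "baseline values for CK-MM and CK-MB will be defined as the last non-missing observation prior to the first administration of ASP0367".
- Section 6.8.1 of the 52-week SAP restricts its data to those before the first open-label dose. The 76-week SAP has no such restriction when it picks the switchers' baseline.

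**The concern.** For a switcher, baseline should be the last state on placebo, and the stated algorithm does not guarantee that. If the selected value was taken on ASP0367, any effect already present is subtracted from every later change, so changes from baseline shrink.

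Criteria that use baseline as a reference move as well. For liver tests, section 6.5.2.1 says "If the baseline value is above ULN then use the baseline value instead of ULN". The skeletal-muscle event of special interest uses five times ULN or baseline CK, whichever is higher, and the cTnT criterion uses baseline when that is above ULN. Total CK and cTnT are outside the CK-MM and CK-MB exception, and protocol section 2.3.1.1 names heart and skeletal muscle as the target organs of toxicity.

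The rule also fails in the other direction. A switcher with no value in days 351 to 378 has no week-52 baseline, even if an earlier pre-drug value exists.

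**Working it through.** **Inputs.** From the 76-week SAP, section 6.8.1: scheduled days 337 (week 48), 365 (week 52) and 393 (week 56); the week-52 window; the nearest-value, tie and same-day rules. From section 6.5.2.1: the liver reference rule. The day of the first open-label dose is not given, so it is varied below.

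**Reproducing the window.** Midpoints between scheduled visits give (337 + 365)/2 = 351 and (365 + 393)/2 − 1 = 378. This matches the SAP. The length is 378 − 351 + 1 = 28 days.

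**When an on-drug value displaces a pre-dose value.** Let p be the day of the pre-dose value and d the day of a later on-drug value, both in the window. The rule picks d if |d − 365| < |p − 365|, or if the two distances are equal and d is the later day. For p < 365 this means any d after p, up to 730 − p. For p ≥ 365 any later d is further from 365, so it is never picked. With the pre-dose value taken on the switch day:

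| Switch day (p) | On-drug days that displace the pre-dose value |
|---|---|
| 362 | 363 to 368 |
| 363 | 364 to 367 |
| 364 | 365 to 366 |
| 365 or later | none |

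Example: switch on day 362 and a repeat test on day 366. |366 − 365| = 1 is less than |362 − 365| = 3, so the day-366 value becomes baseline after four days on drug.

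**Two further routes.** If the window holds no pre-dose value, the nearest on-drug value up to day 378 becomes baseline. If a post-dose value exists on the same day as the selected pre-dose value, the two are averaged (continuous) or the worse is taken (categorical).

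**Where the displaced time goes.** The week-56 window starts on day 379. For a switch on day 365, values on days 366 to 378 therefore belong to week 52, which is the baseline visit, and to no post-switch week. The broad End of Treatment window (days 2 to 560) could take such a value only if nothing nearer day 533 exists.

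**Effect on thresholds (illustrative values, not trial data).** With a baseline of b × ULN and b > 1, a liver criterion of k × ULN becomes k × b × ULN. For b = 1.5, the > 3×ULN criterion is met only above 3 × 1.5 = 4.5×ULN; for b = 2, above 3 × 2 = 6×ULN. A value that is itself the baseline cannot exceed itself, so it would not count even as > ULN. For total CK with b = 1.5, the limit becomes 5 × 1.5 = 7.5×ULN.

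**The case against.** The intent is plainly a pre-drug value. The key-terms table says so, and section 6.8.1 lists the switchers' baseline separately from the visits at and after the first ASP0367 dose. That stands as evidence of intent, but the selection steps that a programmer would code contain no such condition.

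The failure needs unusual timing. The analysis-window table has no visit between weeks 52 and 56, so a competing value would have to be unscheduled, repeated or late. Under protocol version 9.0, participants attend visits before taking product (section 6.1), and in Table 6 dosing follows the assessments, apart from pharmacokinetic sampling. If version 7.0 worked the same way, scheduled week-52 values are pre-dose and same-day post-dose safety values would be rare. This stands, and it limits the number affected.

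CK-MM and CK-MB are reflex tests (protocol Appendix 6), which may explain their separate rule. That is plausible, though the SAP gives no reason. The rule remains a workable model for the other parameters.

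Two stronger readings are tempting. A reader might infer that the protocol forbids the week-52 rule, because section 9.4.1 says "Baseline will be defined as the last non-missing observation prior to first administration of IP, unless otherwise specified". It does not: placebo is itself investigational product (Table 4), so for a switcher that sentence points to week 0, and it allows exceptions. A reader might also take the 378 − 365 = 13 window days after a day-365 switch as the share at risk. They are not: in that case a day-365 pre-dose value is never displaced by a later day.

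**Conclusion.** The gap is real. The stated rule can select an on-drug baseline, against the SAP's own definition, when the switch with its pre-dose value falls on day 364 or earlier and a repeat test lies nearer day 365 (or ties and is later), when no pre-dose value lies in the window, or when a same-day post-dose value is mixed in. Otherwise it gives the right answer. Probably few participants are affected. The number cannot be computed, because neither the switch dates nor the version 7.0 schedule is in the documents.

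A reader might infer that early drug effects are hidden across the safety analysis. The documents do not support that. Treatment-emergent adverse events, the ULN-based counts of troponin, amylase and lipase elevations, and the absolute QTcF categories do not use this baseline, and the 76-week SAP contains no efficacy analysis. Exposed are the switchers' change-from-baseline summaries (laboratory other than CK-MM and CK-MB, vital signs, ECG, weight), the liver criteria, and the total CK and cTnT criteria for events of special interest. The direction is toward smaller changes and fewer flags if an effect has begun by the time of the selected value. The documents give plasma steady state at about four days (protocol section 2.2.3.2), but not how fast these measures respond.

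**What to change.** In the 76-week SAP, sections 6.8.1 and 6.5.5.1 and the Table 1 footnote, define baseline for the Placebo to ASP0367 group, for every parameter, as the last non-missing value taken before that participant's first ASP0367 dose. This extends the section 6.5.2 rule. State how values on the dosing day are treated when no clock time is recorded. Start the first post-switch window at the first ASP0367 dose, so that on-drug values before day 379 count as post-switch data.

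The cost is a short wording change and a small change to the baseline and visit derivations, using data already collected. The downside is that an older pre-drug value serves as baseline when none lies near week 52. Those cases can be listed with the age of the value. If the database is already locked, record the change in the clinical study report, as section 1 of the SAP provides.
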